# Pregnancy

Subjects who are prematurely terminated from the study will be followed to monitor safety for a minimum of 30 days or until resolution of the disqualifying event, whichever is longer, or until the Independent Safety Monitor, the CPI Director of Medical Affairs and the Principal Investigator determine that the follow-up is complete.

Subjects with early termination from this study will not be replaced.

# 9.2 Study or Site Termination

If the Sponsor, Investigator, Independent Safety Monitor, Study Monitor, or appropriate regulatory officials discover conditions arising during the study that indicate that the study should be halted or that the study center should be terminated, this action may be taken after appropriate consultation among the Sponsor, Investigator, Independent Safety Monitor, and Study Monitor.

Conditions that may warrant termination of the study include, but are not limited to, the following:

- The discovery of an unexpected, serious, or unacceptable risk to the subjects enrolled in the study
- A decision on the part of the Sponsor to suspend or discontinue testing, evaluation, or development of the product
- A study conducted at a single study site or a single study site in a multicenter study may also warrant termination under the following conditions:
  - o Failure of the Investigator to enroll subjects into the study at an acceptable rate
  - Failure of the Investigator to comply with pertinent regulations of appropriate regulatory authorities
  - Submission of knowingly false information from the research facility to the Sponsor, Study Monitor, or appropriate regulatory authority
  - o Insufficient adherence to protocol requirements

Study termination and follow-up will be performed in compliance with the conditions set forth in the International Conference on Harmonization (ICH) sixth efficacy publication (E6) on Good Clinical Practice, section 4.12, ICH E6 4.13, ICH E6 5.20, and ICH E6 5.21.

#### 10 ADVERSE EVENTS

Adverse events will be captured in the CRF for this study.

# 10.1 Definitions

# **10.1.1** Adverse Event Definitions

Adverse events are defined according to ICH Harmonized Tripartite Guideline E2A and 21 CFR 312.32.

Adverse event (AE) – is any untoward medical occurrence in a subject or clinical trial subject administered a trial product and which does not necessarily have a causal relationship with this treatment.

An adverse event can therefore be any unfavorable and unintended sign (including an abnormal laboratory finding, for example), symptom, or disease temporally associated with the use of a medicinal product, whether or not considered related to the medicinal product.

The following is not considered or documented as an AE in study records:

- Pre-planned procedure (documented as concomitant illness on the CRF at screening) unless the condition for which the procedure was planned has worsened from the first trial-related activity after the subject has signed the informed consent form.
- Pre-existing conditions found as a result of screening procedures unless the condition worsens during treatment.
- Events which are pre-defined as part of the efficacy analysis. However, if events are serious as defined below, events must be reported as such.

Serious adverse event (SAE) – is any untoward medical occurrence or effect that at any dose: results in death; is life-threatening (this refers to an event in which the subject was at risk of death at the time of the event; it does not refer to an event that hypothetically might have caused death if it was more severe); requires in-subject hospitalization or prolongation of existing hospitalization; results in persistent or significant disability or incapacity; is a congenital anomaly or birth defect; is judged medically important (this refers to an event that may not be immediately life-threatening or result in death or hospitalization, but may jeopardize the subject or may require intervention to prevent one of the other outcomes listed).

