#### **Endpoints:**

Efficacy: SNOT-22, ACQ-7, FEV1, UPSIT, FeNO, PNIFR and TNSS

**Safety, tolerability and other exploratory endpoints:** vital signs, adverse events (AE), physical examination, clinical laboratory tests and biomarkers.

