#### **Analysis Population:**

All subjects who received at least one dose of study medication will be included in the Safety Population. All safety data, including AEs, laboratory parameter, vital signs, FEV1 and physical examinations, will be summarized for subjects in the Safety Population.

The Intent-To-Treat (ITT) Population will consist of all treated subjects with at least one post-baseline assessment of SNOT-22. The Per Protocol (PP) Population will consist of all subjects in the ITT population with no major protocol violations, including violation of inclusion or exclusion criteria or insufficient dosing. All efficacy analyses will be performed for both the ITT and PP Populations. Summary statistics will be presented for each corresponding analysis.

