# 6.4 Secondary Efficacy Endpoints and Other Exploratory Endpoints

# 6.4.1 Second and Exploratory Efficacy Endpoints

- Subject reported symptoms:
  - Asthma Control Questionnaire (ACQ-7)
  - Total Nasal Symptom Score (TNSS)
- FEV1 and peak Nasal Inspiratory Flow Rate (PNIFR)
- University of Pennsylvania Smell Identification test (UPSIT)
- Frequency and severity of asthma exacerbations and chronic sinusitis
- Use of rescue medication and antibiotic use
- Urinary leukotriene E4 and PG metabolite levels
- Serum leukotriene B4 levels
- Blood eosinophil count
- Fractional exhaled Nitric oxide (FeNO)
- Nasal epithelial, urinary and plasma eicosanoid levels

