## 11.6.4 Safety Parameters

All safety data will be summarized. AEs will be coded using the Medical Dictionary for Regulatory Activities (MedDRA) (Version 9.0 or later). All Treatment Emergent Adverse Events (TEAEs) will be summarized by treatment group. Counts and percents will be presented by treatment group for each observed system organ class (SOC) and preferred term as defined in MedDRA.

The preferred terms and SOCs will be summarized in the following set of tables:

- All AEs;
- All AEs by maximum level of intensity;
- All AEs by closest relationship to the study medication.

The frequencies and percentages of AEs will be tabulated. Incidence, relation to study medication, and severity will be summarized.

Physical examination findings, laboratory parameters, vital signs, FEV1, weight, and corresponding changes from Baseline, as appropriate, will be summarized using descriptive statistics at each visit.

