 - CFB ACQ = post-treatment measurement – baseline
 - Any improvement in ACQ-7 (Yes or No): If CFB ACQ<0, then improvement =’Yes’; otherwise improvement = ‘No’
- Total Nasal Symptom Score (TNSS) AM and PM measurements
 - TNSS Daily Score = sum of the 4 symptom scores (congestion, runny_nose, nasal_itching, sneezing) for both AM and PM, separately. (listed only)
 - TNSS Visit Score: The daily score for AM and PM are averaged over time between the visits separately. Baseline Visit Score for AM and PM is obtained by averaging over the screening period and the day of the baseline visit. Week 4 Visit Score is obtained by averaging over the day after the baseline visit to the day of the Week 4 visit. Week 8 Visit Score is obtained by averaging over the day after Week 4 visit to the day of the Week 8 visit. Week 10 Visit Score is obtained by averaging over the day after Week 8 visit to the day of Week 10 visit.
 - CFB TNSS Visit Score = post-treatment measurement – baseline
- Frequency and Severity of Asthma Exacerbations (Respiratory Reaction Questionnaire)
 - Subject Frequency =count the number of reports since the previous visit for each visit
 - CFB Frequency = post-treatment measurement – baseline
 - Max Severity= define the maximum severity for each subject (none, mild, moderate, or severe) over the period since the previous visit.
 - Inhaler or rescue med (number of reports) count= count the number of reports where resp_rxn_inhaler >0 OR resp_rxn_add_tx_yn=Yes
 - CFB Inhaler or rescue= post-treatment measurement – baseline

- Frequency and Severity of Chronic Sinusitis (Sinus Infection Questionnaire)
 - Antibiotic use Frequency (number of reports) count= count the number of reports over the period since the previous visit where sinus_inf_antibio=yes
 - CFB Antibiotic use= post-treatment measurement – baseline

Pharmacodynamic Variables and biomarkers

- Plasma - Data from third party vendor
 - ScD10L (pg/mL)
 - Sp_selection (ng/mL)
- Biomarkers - Data from third party vendor.
 - Urine LTE4 (ng/mg Creatinine)
 - Urine PGD-M (ng/mg Creatinine)
 - Urine TX-M (ng/mg Creatinine)
 - Plasma F2 Isoprostanes (ng/mL)
 - Serum LTB4 (ng/mL)
 - SAM-Eicosanoids PGD2 (ng/mL)
 - SAM-Eicosanoids PXA2 (ng/mL)
 - SAM-Eicosanoids F2 Isoprostanes (ng/mL)

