7 EFFICACY ANALYSES

All hypothesis tests will be performed at the 0.05 level. Analyses of the primary efficacy variables will be performed using both the ITT and PP Populations; analyses of secondary efficacy variables will be performed using the ITT population only. Summary statistics will be presented for all analyses of efficacy variables.

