8.3 Vital Signs

Vital signs (heart rate, respiratory rate, systolic blood pressure, diastolic blood pressure and weight, and BMI) will be presented in a table with summary statistics by visit for the Safety Population. Height will be summarized for the Screening visit.

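### The SAP omits the FEV1 safety summary that the protocol calls for, and a non-serious exacerbation in a treated subject outside the ITT set is counted in no by-arm event table

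*Protocol*

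**What the plan says.** **FEV1.** The protocol gives it two roles. The synopsis endpoint list names it as efficacy: "Efficacy: SNOT-22, ACQ-7, FEV1, UPSIT, FeNO, PNIFR and TNSS". The synopsis paragraph on analysis populations names it as safety: "All safety data, including AEs, laboratory parameter, vital signs, FEV1 and physical examinations, will be summarized for subjects in the Safety Population". Protocol 11.6.4 (Safety Parameters) repeats the safety role, listing "Physical examination findings, laboratory parameters, vital signs, FEV1, weight, and corresponding changes from Baseline" for descriptive summary at each visit. The protocol is not uniform on this: the safety list in the synopsis endpoints and the safety endpoints in Section 6.4.2 both leave FEV1 out.

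SAP Section 8 covers adverse events, clinical laboratory tests, vital signs, physical examination, and PT/INR. FEV1 is in none of its subsections. It appears in the SAP 7.2 chart, with both its value and its change from baseline marked ITT and LOCF. SAP Section 7 states that "analyses of secondary efficacy variables will be performed using the ITT population only". SAP Section 9 declares that restriction as the only change from the protocol.

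**Exacerbations and sinusitis.** Among the items that are not documented as adverse events, Protocol 10.1.1 lists: "Events which are pre-defined as part of the efficacy analysis. However, if events are serious as defined below, events must be reported as such". Protocol 6.4.1 includes "Frequency and severity of asthma exacerbations and chronic sinusitis" among the efficacy endpoints, and SAP 4.6 defines both as efficacy variables. SAP 7.2 tabulates their reports and maximum severity in ITT with LOCF. SAP 4.7 limits ITT to treated subjects who have a SNOT-22 score after baseline.

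**The concern.** There are two separate gaps.

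The first is a safety summary that the protocol states and the SAP neither contains nor declares as dropped. Any treated subject who is outside ITT but has spirometry after baseline would be in no FEV1 table.

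The second comes from two rules acting together. The adverse event rule takes non-serious exacerbations out of the AE tables, and the ITT rule takes subjects without a later SNOT-22 out of the exacerbation table. A subject caught by both has the event counted in neither.

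The second loss need not be random. Under Protocol 9.1, if the investigator stops study medication during an asthma exacerbation, the subject is withdrawn from the study. Table 8–1 schedules the first SNOT-22 after baseline at Week 4; Week 1 is a telephone contact. An early exacerbation can therefore be the reason a subject is missing from the only by-arm table that counts exacerbations. If the arms differ in such exits, the comparison of respiratory tolerability is incomplete in the place where it would be most informative.

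**Working it through.** The plan states no figure on this point, so the main check is to set the texts side by side.

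**Step 1: FEV1**

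| Source | Role of FEV1 | Population and method |
|---|---|---|
| Protocol synopsis, endpoints | Efficacy; absent from the safety list | Not stated there |
| Protocol synopsis, analysis population | Safety | Safety Population |
| Protocol 6.4.2 | Absent from the safety endpoints | Not applicable |
| Protocol 11.6.4 | Safety | Descriptive, value and change, each visit |
| SAP 7.2 | Efficacy | ITT, LOCF, Weeks 0, 4, 8, 10 |
| SAP 8.1 to 8.5 | Absent | None |
| SAP 9 | Not mentioned | Declares only ITT for secondary variables |

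Two protocol passages call for the summary and two safety lists omit FEV1. The SAP follows the lists and does not say so. The declaration in SAP Section 9 concerns the population for secondary efficacy variables; it does not cover removal of a safety summary.

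**Step 2: where a non-serious exacerbation can be counted**

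1. AE tables (SAP 8.1, Safety Population): excluded by Protocol 10.1.1 if the event counts as pre-defined for efficacy. That section names no events, so applying it to exacerbations is an inference, but a direct one from Protocol 6.4.1 and SAP 4.6.
2. Exacerbation table (SAP 7.2): counted only if the subject is in ITT.
3. Disposition table (SAP 6.1, Safety Population): shows a reason for early termination, not an event.
4. Concomitant medication listing (SAP 6.4) and the general data listings (SAP 5): the event or its treatment may be visible, but nothing is summarised by arm.

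For a treated subject with no later SNOT-22, items 1 and 2 both fail and only items 3 and 4 remain.

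**Step 3: size, by illustration only**

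The 38 per arm is from Protocol 11.1. The rest is assumed: 8 subjects in the arm have a non-serious exacerbation, and k of those 8 leave with no SNOT-22 after baseline. All other subjects are taken to be in ITT.

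True proportion = 8/38 = 21.1%. Proportion visible in ITT = (8 − k)/(38 − k).

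| k | Visible in ITT | Percent |
|---|---|---|
| 0 | 8/38 | 21.1 |
| 1 | 7/37 | 18.9 |
| 2 | 6/36 | 16.7 |
| 3 | 5/35 | 14.3 |
| 4 | 4/34 | 11.8 |

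With k = 2 the understatement is 21.1 − 16.7 = 4.4 percentage points; with k = 4 it is 21.1 − 11.8 = 9.3. With k = 0 there is none. The documents give neither the number of exacerbations nor k.

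**The case against.** Much can be said for the plan.

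- **Serious events are kept.** Protocol 10.1.1 requires serious events to be reported even when they are efficacy events, and its definition of serious includes medically important ones. Respiratory adverse events that are not efficacy events also stay in the AE tables. A reader might infer that respiratory worsening has no Safety Population table at all; the documents do not support that. The gap concerns non-serious efficacy events and FEV1.
- **The SAP did not move FEV1 or invent the rules.** FEV1 was already an efficacy endpoint in the protocol, Protocol 11.5 already prescribes LOCF for continuous data, and the adverse event exclusion is the protocol's own. A reader might infer that the whole arrangement departs from the protocol. Only the missing FEV1 safety summary does, and there the protocol's own safety endpoint lists give the SAP some cover.
- **Exit assessments limit the loss.** Protocol 8.1 asks for the End of Treatment assessments at premature discontinuation, and these include SNOT-22 and spirometry. An event is lost only if an exacerbation, an exit before any later SNOT-22 and a missed exit assessment coincide. This stands, and it is why the number is probably small. It does not bring the number to zero: Protocol 9.1 asks sites to try to obtain final assessments and cannot guarantee them.
- **LOCF does not generally hide a decline.** SAP 5.1 applies it only when there is a measurement after baseline, so baseline is not carried forward. A worsened exit value would itself be carried forward. LOCF conceals only a decline that comes after the last measurement, so it is not a reason to change the efficacy tables.
- **Respiratory safety may not be the leading risk.** The potential risk named in Protocol 5.5 is bleeding, and Protocol 5.4 reports no respiratory reactions caused by ifetroban alone. However, the Week 1 call in Protocol 8.1.2 is there partly to check for worsening asthma, so the question is not foreign to the plan.
- **Version and shells.** The SAP cites a protocol dated 24 January 2017 and differs from the supplied protocol elsewhere, for example on screening length. Its table shells are to come with the final version. A version mismatch may explain the FEV1 gap, but the texts still need reconciling.

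**Conclusion.** The point holds in two parts of different strength.

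The FEV1 part rests on the text alone. The protocol states a safety summary in two places, SAP Section 8 omits it, and SAP Section 9 is silent. The protocol's two safety endpoint lists must be reconciled with its synopsis population paragraph and Section 11.6.4.

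The exacerbation part rests on reading Protocol 10.1.1 as covering exacerbations and sinusitis. On that reading, a non-serious event in a treated subject without a SNOT-22 after baseline is counted in no by-arm event table. No passage promises such events in a Safety Population table, so this is a gap in coverage and not a contradiction. The number affected cannot be derived from the documents and is probably small. The illustrated range of 18.9% down to 11.8% against 21.1% depends wholly on assumed inputs.

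Neither part touches the primary analysis, the sample size or the type I error rate.

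**What to change.** Add two descriptive tables to SAP Section 8, for the Safety Population, by arm, on observed data:

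1. FEV1 and its change from baseline by visit, with a separate row for exit spirometry in early discontinuers. Without that row, an observed-data table would drop a worsened exit value.
2. Number and percentage of subjects with an asthma exacerbation, and with a sinus infection, by maximum severity. SAP 4.6 defines maximum severity for asthma only; SAP 7.2 has a maximum severity row for sinusitis that 4.6 does not define, so that grading should be stated.

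Keep the ITT/LOCF efficacy tables as they are. Reconcile the protocol's safety endpoint lists with its synopsis population paragraph and Section 11.6.4. If the sponsor decides against the FEV1 safety summary, record that in SAP Section 9.

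The cost is two extra tables from data already collected, with no new visits, tests or subjects. The change should be made before unblinding.

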# **10.1.2** Adverse Event Assessment Definitions

# **Severity**

The maximum severity of an adverse event is assessed by the investigator using the following definitions:

- Mild: Transient symptoms, no interference with the subject's daily activities.
- Moderate: Marked symptoms, moderate interference with the subject's daily activities.
- Severe: Considerable interference with the subject's daily activities, unacceptable.

# Relationship

The causal relationship between an adverse event and the trial product is assessed by the investigator using the following definitions:

- Probable: Good reasons and sufficient documentation to assume a causal relationship.
- Possible: A causal relationship is conceivable and cannot be dismissed
- Unlikely: The event is most likely related to an etiology other than the trial product.

An adverse event is considered causally related to the use of the trial product when the relationship assessment is probable or possible. Events assessed as unlikely related to the use of trial product will generally be considered as having no relationship to treatment.

#### Outcome

The outcome of an adverse event is assessed by the investigator using the following definitions:

- Recovered: Fully recovered, or by medical or surgical treatment the condition has returned to the level observed at the first trial-related activity.
- Recovering: The condition is improving and the subject is expected to recover from the event. This term should only be used when the subject has completed the trial.
- Recovered with sequelae: As a result of the AE the subject suffered persistent and significant disability/incapacity (e.g. became blind, deaf, paralyzed). Any AE recovered with sequelae should be classified as SAE.
- Not recovered: The subject's condition has not improved and the symptoms are unchanged

- Fatal
- Unknown: The subject's condition is unknown. This term should only be used when no other definition is possible (e.g. the subject is lost to follow-up).

# 10.2 Collection, Recording and Reporting of Adverse Events

For this study, all events meeting the definition of an adverse event must be collected and reported from the first trial-related activity after the subject signs the informed consent and until end of post-treatment period.

The investigator should record the diagnosis, if available. If no diagnosis is available the investigator should record each sign and symptom as individual adverse events.

The investigator must report initial information on all serious adverse events within 24 hours of obtaining knowledge of the event. Furthermore, the investigator must complete the SAE forms within five days of obtaining knowledge of the SAE. The monitor must be informed accordingly.

The investigator must inform the IRB in accordance with local requirements in force and the ICH guidelines for GCP and the Food and Drug Administration (FDA) Title 21 Code of Federal Regulations, Part 312.32.

# 10.3 Follow-up of Adverse Events

All adverse events classified as non-serious adverse events that are both classified as severe and possibly or probably related to the investigational medicinal product must be followed until the subject has recovered and all queries have been resolved.

For cases of chronic conditions, follow-up until "recovered" is not required. After the subject has completed the trial, these cases can be closed with the outcome "recovering" or "not recovered".

All other non-serious adverse events must be followed until the outcome of the event is "recovering" (for chronic conditions), "recovered" or until the last subject contact/visit/end of post-treatment follow-up period, whichever comes first, and until all queries related to the adverse event have been resolved

## **Follow-up of Serious Adverse Events**

All adverse events classified as serious should be followed until the outcome of the event is "recovered", "recovered with sequelae", or "death" and until all queries have been resolved. For cases of chronic conditions and cancer, follow-up until "recovered", "recovered with sequelae" or

"death" is not required. After the subject has completed the trial, these cases can be closed with the outcome "recovering" or "not recovered".

#### 11 STATISTICAL METHODS AND DATA ANALYSIS

The following text provides general description of the statistical methodology for the assessment of efficacy, safety, and tolerability of 200 mg/day of oral ifetroban in this double-blind placebo-controlled study in subjects with symptomatic AERD. Details of the statistical analyses will be provided in the Statistical Analysis Plan, which will be finalized prior to database lock and unblinding. All recorded data will be listed.

